6.6.1.2 Handling of Missing Data

Missing data will not be imputed in the primary analysis; participants missing either baseline BCVA or 12-week BCVA, or with an out-of-window 12-week visit will not be included. A sensitivity analysis will be performed to assess the impact of missing data. A supportive analysis will be conducted including available data from out of window visit assessments.

6.6.1.3 Sensitivity Analysis

A sensitivity analysis will be conducted using multiple imputation for missing data and results of the analysis will be assessed for consistency with the primary analysis. Imputation will be based on regression methods using significant baseline covariates as independent predictors. Covariates will be determined based on a statistically or clinically significant association with the change in BCVA.

Missing data will be imputed using the PROC MI procedure in SAS. PROC MI imputes missing covariates in the order variables are listed on the VAR statement. The variables will be listed on the VAR statement in the order listed above.

Missing covariates will be imputed using Markov Chain Monte Carlo (MCMC) methods. For the endpoint, the method will be determined based on the pattern and nature of the missing data (e.g. FCS regression method for an arbitrary missing pattern). The imputation will be executed in two steps in SAS. The first step will use PROC MI to impute the missing covariates. For each imputed dataset generated in step 1, the endpoint status will be imputed in step 2 to create the final imputed datasets.

Explorations to omit predictors may be conducted if the multiple imputation models will not converge. For each multiple imputation model, 10 imputed datasets will be generated. The imputed datasets will then be combined for inference using standard methods such as those available in SAS PROC MIANALYZE or other valid statistical software.

If no significant predictors are identified, the following method for imputation will be used. Participants who completed the study will be categorized by age, sex, and treatment received. For a participant with missing data, the imputed value will be a random draw from those participants with data that have the same age, sex, and treatment.

Additional sensitivity analyses may be performed if deemed necessary.

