For beta spending, rho was set to 1.0 which results in a spending function much like the Pocock method (i.e. equal spending between the interim and final analyses). For alpha spending, rho was set to 2.0 resulting a spending function somewhere between that found for the O'Brien-Fleming method and the Pocock method.

The planned interim analysis will also involve an analysis of the primary safety endpoint, including both the test of noninferiority in mean fellow eye BCVA change between groups, and a report of the frequency and severity of all related Adverse Events (anticipated and unanticipated).

Sample Size Estimation

Statistical Analysis Plan		Page 13 of 23
Sponsor Luminopia	Study Luminopia One Amblyopia Vision Improvement Study	

The sample size was calculated using the SEQDESIGN procedure in SAS version 9.3. The alternative reference was set to 0.075 logMAR (0.75 lines). As part of the design statement, the number of analyses was set to 2 where the first analysis was planned after 75% of the expected participants complete their 12-week primary outcome visit, and the second after all participants complete their 12-week primary outcome visit. The method of alpha spending was set to “errfuncpow(rho=2.0)” and the method of beta spending was set to “errfuncpow(rho=1.0).” The “alt” parameter was set to “upper” to indicate a one-sided test, alpha was set to 0.05, and beta was set to 0.10 in order to achieve 90% power. The “stop” parameter was set to “both” in order to have boundaries for both success and futility.

This specification results in an effective sample size of 132 participants (66 per arm) providing 90% power to detect a 0.075 logMAR difference between the therapeutic and control groups using a one-sided test (primary **efficacy** endpoint).

With an equal beta-spending function, if there truly is no treatment effect favoring Luminopia One, the chance of stopping the study early for futility at the interim analysis is approximately 89%.

The primary **safety** endpoint will test noninferiority in fellow eye visual acuity change from baseline to the 12-week primary endpoint. The sample size required to achieve 90% power, for a non-inferiority window of 1.0 line of VA (-0.10 logMAR) with Type I error rate of 0.05, is fewer than 132 participants. Therefore, the primary efficacy endpoint will be used to drive sample size.

Adjusting the effective sample size for a 5% loss to follow-up results in a target enrollment of **140 participants**.

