6.3 Handling of Missing Data

Multiple imputation for missing data will be performed as a secondary approach with the ITT population, and results of the analysis with imputation of missing data will be considered supportive in nature and assessed for consistency with the primary analysis. Imputation will be based on regression methods using baseline covariates as independent predictors. If no significant predictors can be found, the following method will be used. Those participants completing the study will be categorized by age, sex, and treatment received. For a participant with missing data, the imputed value will be a random draw from those participants with data that have the same age, sex, and treatment. See Section 6.6 for imputation methods specific to the study endpoints.

In the case of partial dates (e.g. adverse event onset date), the unknown portion of the date of the event will be imputed. If the month and year are known, the 15th of the month will be used for analysis. If only the year is known, the event will be analyzed as if it occurred on June 30th of the known year. Imputation of partial dates is participant to the condition that it must occur on or after the randomization date. In the case where the imputed date is prior to the randomization date, the date of the randomization will be used.

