6.6.2 Primary Safety Endpoint

The co-primary analysis of safety will test if the mean change in fellow eye visual acuity of the therapeutic group from baseline to 12 weeks is non-inferior to the mean change in fellow eye visual acuity of control group within a margin of 0.10 logMAR. The formal hypothesis being tested are:

$$H_0: \mu_{\text{therapeutic}} - \mu_{\text{control}} \geq \delta$$

Statistical Analysis Plan		Page 18 of 23
Sponsor Luminopia	Study Luminopia One Amblyopia Vision Improvement Study	

$$H_a: \mu_{\text{therapeutic}} - \mu_{\text{control}} < \delta$$

where μ is the change from baseline (follow-up - baseline) for both the control and therapeutic participants and δ is the non-inferiority window of 0.10 logMAR. The statistical test is a two-sample one-sided T-test which will be done at the 0.05 level of significance. An upper 95% confidence limit for the difference will also be presented. The endpoint will be considered met if the p-value is < 0.05 .

The endpoint will be evaluated using the ITT population with no imputation for missing data. Assessments from out of window visits will be considered missing in the primary analysis. Supplementary analysis will be provided based on ITT with imputation, PP and AT cohorts, as described in the primary efficacy endpoint analysis.

In addition to the formal test on the mean change in fellow eye visual acuity, the primary safety endpoint will report the frequency and severity of all related Adverse Events (anticipated and unanticipated). Count of events, percent of participants who experienced an event, and an exact 95% confidence interval of the event rates will be presented for each treatment group by event type. No formal hypothesis testing will be performed. Event rates will be summarized for clinical interpretation. Safety analyses on Adverse Events will be based on the AT analysis cohort.

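### The multiple-imputation model in SAP 6.3 and 6.6.1.3 does not name randomised arm and points to a variable list that is absent; run as written, it shrinks the between-arm difference by about the missing fraction.

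*SAP*

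**What the plan says.** The primary efficacy model (SAP 6.6.1.1) regresses change in amblyopic-eye BCVA on treatment arm and nothing else. It uses the ITT set without imputation. Multiple imputation is the planned supportive check, to be judged for consistency with the primary result.

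- **General rule (6.3):** "Imputation will be based on regression methods using baseline covariates as independent predictors".
- **Rule for this endpoint (6.6.1.3):** "Imputation will be based on regression methods using significant baseline covariates as independent predictors". The covariates are chosen later: "Covariates will be determined based on a statistically or clinically significant association with the change in BCVA".
- **PROC MI variables (6.6.1.3):** "The variables will be listed on the VAR statement in the order listed above". No list appears above that sentence or elsewhere in the SAP.
- **Fallback if no predictor is significant (6.3, 6.6.1.3):** "Participants who completed the study will be categorized by age, sex, and treatment received", and "the imputed value will be a random draw from those participants with data that have the same age, sex, and treatment".
- **Fellow eye (6.6.2):** "Supplementary analysis will be provided based on ITT with imputation, PP and AT cohorts, as described in the primary efficacy endpoint analysis".

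Treatment therefore appears in the fallback only, and there as the treatment received.

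**The concern.** Randomised arm is a design factor, not a baseline covariate, so a programmer who follows the regression rule literally leaves it out. The imputation model then assumes no treatment effect among participants with missing values, while the analysis model exists to estimate that effect. The two are incompatible, and the estimate is pulled towards zero even when data are missing completely at random.

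This is the planned check on values that were never collected; the separate out-of-window analysis (6.1.3, 6.6.1.2) covers only early or late visits. For efficacy, a weaker imputed result could be misread as sensitivity to missing data when the method itself caused it. For fellow-eye non-inferiority, shrinkage makes passing easier if the device arm's fellow eye truly does worse.

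There are two smaller points:

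- BCVA at 4 and 8 weeks is collected (3.3.3, 6.6.4.3) but is not in the imputation model. This loses information and, if dropout depends on early response, can bias the result in either direction.
- Treatment received is not defined for imputation. Its nearest definition is the as-treated set (6.2), which counts device-arm participants with adherence of 25% or less as controls. On that reading, some device-arm participants would be imputed from controls in an analysis by randomised arm.

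**Working it through.** **Inputs from the SAP.** Section 5: efficacy difference -0.075 logMAR, SD 0.140; fellow-eye SD 0.10 and margin 0.10; expected fellow-eye changes -0.05 and -0.02; loss to follow-up 5%; one-sided alpha 0.05; power 90%. **Assumed:** missing rates of 10%, 15% and 20%, and all correlations.

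**The plan's own figure.** With alpha spending 0.05t², beta spending 0.10t, an interim look at t = 0.75 and binding futility, the drift is 3.066. Per arm, n = 2 × (0.14 × 3.066 / 0.075)² = 65.5, so 66 per arm and 132 in total, as stated. Then 132 / 0.95 = 138.9, against the stated 140. The check uses 70 per arm. The SAP gives no figure for imputation bias.

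**Shrinkage by formula.** Let d be the true difference, m1 and m0 the missing fractions in the device and control arms, and w the device-arm share of observed participants. Without arm in the model, missing values in either arm have expected value (control mean + w·d), because randomisation balances the baseline covariates on average. Hence

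expected difference = d × [(1 - m1) + (m1 - m0) × w],

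which is d × (1 - m) when m1 = m0 = m.

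- 5%: 0.075 × 0.95 = 0.0713
- 10%: 0.075 × 0.90 = 0.0675
- 15%: 0.075 × 0.85 = 0.0638
- 20%: 0.075 × 0.80 = 0.0600
- 10% device, 0% control: w = 0.90/1.90 = 0.474, factor 0.90 + 0.10 × 0.474 = 0.947
- 15% device, 5% control: w = 0.85/1.80 = 0.472, factor 0.85 + 0.10 × 0.472 = 0.897

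**Simulation.** Settings: 70 per arm, proper regression imputation, 10 sets, Rubin's rules, one baseline covariate (r = 0.3), data missing completely at random, interim look ignored, 3000 to 4000 trials per setting. Ranges are across repeated runs.

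| Missing | Efficacy estimate, no arm | With arm | Chance of p<0.05, no arm | With arm |
|---|---|---|---|---|
| 5% | -0.071 to -0.072 | about -0.075 | 90–92% | 92–93% |
| 10% | -0.067 to -0.068 | about -0.075 | 88% | 91% |
| 20% | -0.060 | about -0.075 | 76–77% | 87% |

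With r = 0.4 the estimates without arm are -0.0705, -0.0676, -0.0639 and -0.0599 at 5%, 10%, 15% and 20% missing.

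**Fellow eye, true deficit equal to the margin (+0.10).** Without arm the estimate is 0.10 × (1 - m) = +0.095, +0.090 and +0.080 at 5%, 10% and 20%. The imputed analysis then passes wrongly in about 8%, 10–12% and 21–24% of trials, against about 5% with arm. At the SAP's expected difference, -0.05 - (-0.02) = -0.03, both models pass in essentially all trials.

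**Omitting 4- and 8-week BCVA, with arm in the model.** Assumptions: 8- to 12-week correlation 0.7; dropout confined to the worse half of 8-week responders in one arm and random in the other. At 5%, 10% and 20% missing the estimate is -0.079, -0.083 and -0.092 if they leave the device arm, and -0.072, -0.067 and -0.057 if they leave the control arm. Adding the two visits restores about -0.075.

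**The case against.** **The effect is small where it counts.** The imputed results are supportive; both co-primary tests run without imputation and alone decide success (6.6.3). At the SAP's only missing rate, "Adjusting the effective sample size for a 5% loss to follow-up results in a target enrollment of" 140, the shift is about 0.004 logMAR. A primary pass with a failed arm-free imputed analysis occurred in 1.4% of simulated trials, against 0.4% with arm. In the fellow-eye scenario the deciding test, without imputation, still passes wrongly only about 5% of the time. All of this stands, and it limits the weight of the point.

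**Arm is not expressly excluded.** The endpoint imputation method is left partly open, and the fallback conditions on treatment, which suggests an intent to impute within treatment. A programmer might add arm. But the predictors are stated as baseline covariates in two places, and the list that could settle the matter is missing. Naming treatment in the fallback alone makes it harder to read as implied in the main route.

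**The higher missing rates are assumed.** This is correct. Out-of-window visits count as missing in the primary analysis (6.6.1.1), which could push the rate above 5%, but the SAP does not say whether the imputed analysis discards those values too.

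**The 4- and 8-week scenario is built to show its result.** Dropout was generated from 8-week response, so including that visit must remove the bias. It shows what could be lost under such dropout, not what to expect. Imputing from baseline covariates is a legitimate choice under a missing-at-random assumption. The case for adding these visits is that they are already collected and cost nothing to use.

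**Conclusion.** The concern holds. As written, the regression imputation omits the one term that the analysis model estimates, and the variable list that it relies on is absent. If arm is left out, the difference shrinks by about the average missing fraction: 5% of the effect at the planned loss, and 10% to 20% only if missingness reaches those assumed rates. The direction is conservative for efficacy. It is anti-conservative for fellow-eye non-inferiority only if there is a true deficit. Study success and the type I error of the deciding tests are unaffected. The shrinkage does not arise in the same way in the fallback; its reliance on treatment received is a mismatch with ITT whose effect is probably small and was not quantified. The text should be corrected, because an analysis that moves the estimate under purely random missingness cannot serve as a check on missing data.

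**What to change.** In 6.3 and 6.6.1.3, replace the predictor rule with text such as:

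> Missing 12-week BCVA (each eye) will be imputed separately by randomized arm (or with randomized arm in the model), with VAR variables in this order: baseline BCVA, 4-week BCVA, 8-week BCVA, 12-week BCVA.

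Any further baseline covariates found relevant are added to this fixed set and do not replace it. In the fallback, change treatment received to randomized treatment. It would also help to say whether out-of-window 12-week values are kept or imputed in this analysis.

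The cost is SAP wording and one PROC MI VAR or BY statement. It needs only randomised arm and BCVA from visits already planned. The primary analysis, sample size and conduct do not change.

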6.2 Analysis Populations

The following analysis populations are defined for analysis:

- 1. Intention-to-treat (ITT) Analysis Set:** The intention-to-treat (ITT) population consists of all enrolled participants who were subsequently randomized. The ITT set will be analyzed according to randomized treatment assignment regardless of treatment actually received. The ITT population will not include participants who did not meet eligibility criteria at the time of enrollment and are ultimately deemed ineligible for the study, including participants who are withdrawn from the study due to insufficient internet.
- 2. As-Treated Analysis Set:** The as-treated (AT) population consists of participants enrolled and randomized, however treatment group assignment for the purposes of analysis will be based on the actual treatment received. Participants randomized to the Luminopia One group with ≤ 25% adherence in device use at 12 weeks will be analyzed as control participants.
- 3. Per-Protocol Analysis Set:** The per-protocol (PP) population consists of all ITT participants who were treated according to randomized assignment, who had adherence > 25% in Luminopia One Use for the therapeutic group, and who had no major protocol deviations that could affect the endpoints of interest. Protocol deviations will be reviewed and defined as major prior to analysis

Statistical Analysis Plan		Page 15 of 23
Sponsor Luminopia	Study Luminopia One Amblyopia Vision Improvement Study	

of study outcomes. The 25% adherence threshold for the PP population was determined from pilot trials on Luminopia One, in which all enrolled participants with > 25% adherence and no major protocol deviations showed improvements from using the therapeutic. Adherence will be captured while maintaining masking of the study in accordance with the Masking Plan.

The ITT population will be used for analysis and interpretation of the primary and secondary efficacy endpoints and the co-primary safety endpoint assessing BCVA in the fellow eye. Supportive analysis for the primary and secondary efficacy endpoints will be performed using the PP population to provide insight into the potential impact of protocol deviations on the primary results of the study. The AT cohort will be used to characterize and assess safety, including the co-primary safety endpoint evaluating frequency and severity of all related Adverse Events, as well as supportive efficacy analyses.

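### The fallback imputation for the ITT analysis picks donors by treatment received rather than randomised arm, which can favour fellow-eye noninferiority, and does not say that the draw is repeated

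*SAP*

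**What the plan says.** SAP 6.2 sets the ITT rule: "The ITT set will be analyzed according to randomized treatment assignment regardless of treatment actually received". The primary efficacy and fellow-eye analyses use this set without imputation. An ITT analysis with imputation is a named supplement to both (6.6.1.1, 6.6.2), and 6.6.2 takes its method from the efficacy section. According to 6.3, "results of the analysis with imputation of missing data will be considered supportive in nature".

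The main imputation method is regression on baseline covariates, chosen as follows: "Covariates will be determined based on a statistically or clinically significant association with the change in BCVA". On repetition, 6.6.1.3 says "For each multiple imputation model, 10 imputed datasets will be generated", to be combined by the usual multiple-imputation rules.

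If no predictor qualifies, a donor method replaces the regression. Section 6.6.1.3 says "Participants who completed the study will be categorized by age, sex, and treatment received", and 6.3 says the same: "Those participants completing the study will be categorized by age, sex, and treatment received". For a child with missing data, "the imputed value will be a random draw from those participants with data that have the same age, sex, and treatment".

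The only rule in the SAP that turns actual use into a treatment group is in the As-Treated definition in 6.2: "Participants randomized to the Luminopia One group with ≤ 25% adherence in device use at 12 weeks will be analyzed as control participants".

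**The concern.** There are two defects in one short rule.

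First, the donor groups follow treatment received in an analysis that carries the ITT label. If the As-Treated rule decides what was received, a device-arm child with low use and no usable 12-week value is given a control child's outcome, and a low-use device child with data becomes a possible donor for controls. Both exchanges make the arms look more alike. For amblyopic-eye superiority that is cautious. For fellow-eye noninferiority it can hide harm, because similarity is what the test rewards. The SAP also does not say how treatment received is settled for a child who leaves before the 12-week adherence figure exists.

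Second, the fallback describes a draw but does not say that it is made afresh in each of the ten data sets and combined. If it were made once and the filled-in values analysed as observed, the interval would be too narrow.

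At stake is the plan's named check on missing data for both co-primary endpoints, not the primary result.

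**Working it through.** **Inputs from the SAP.** 140 enrolled at 1:1, so 70 per arm; effective size 132; planned loss 5%; one-sided 0.05; two-sided 90% interval for efficacy (6.6.1.1); efficacy difference 0.075 logMAR with SD 0.140; fellow-eye SD 0.10 and margin 0.10 logMAR; ages 4 to 7.

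**Assumptions.** Values are missing completely at random and in equal share in both arms. The missing share is 5% or 10%; out-of-window visits also count as missing in the primary analysis, so the share can exceed the planned loss. A fraction q of missing device-arm children draw from the control pool. The SAP gives no value for q; 0.5 is used, with the range from 0 to 1 shown.

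**The plan's own figures.** The SAP gives none for the imputation. Its sample size reproduces: a two-look design at 75% information with the stated spending functions and binding futility gives 131.0, so 132 in equal arms. 132/0.95 = 138.9, so 139, or 140 in equal arms.

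**1. Donors from the wrong arm.** Expected shift toward zero = q × missing share × true difference.

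- Efficacy, q = 0.5: 0.5 × 0.05 × 0.075 = 0.002 logMAR at 5% missing and 0.5 × 0.10 × 0.075 = 0.004 at 10%. This works against the device.
- Fellow eye, true difference at the margin of 0.10, q = 0.5: 0.5 × 0.05 × 0.10 = 0.0025 at 5% and 0.0050 at 10%. This works in favour of the device.

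For the fellow eye, with r observed per arm, take the SE as √(2 × 0.10²/r). It is 0.0173 at 5% missing (r = 66.5) and 0.0178 at 10% (r = 63). One-sided Type I error is then approximately Φ(−1.645 + shift/SE):

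| q | 5% missing | 10% missing |
|---|---|---|
| 0 | 5.0% | 5.0% |
| 0.5 | Φ(−1.645 + 0.144) = 6.7% | Φ(−1.645 + 0.281) = 8.6% |
| 1 | Φ(−1.645 + 0.288) = 8.7% | Φ(−1.645 + 0.561) = 13.9% |

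Simulation at q = 0.5 gives about 7.0% to 7.6% at 5% missing and 7.6% to 9.2% at 10%, against about 5% with same-arm donors. Combining ten draws does not remove the excess, because it comes from the donor pool and not from the standard error.

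**2. One draw, if that is what is meant.** With n = 70 per arm, r observed and m missing, the variance of an arm mean is s²[1/r + (m/n²)(1 − 1/r)]. Treating the filled-in data as observed reports s²/n.

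- 5% missing: 1/66.5 + (3.5/4900)(1 − 1/66.5) = 0.01574 against 1/70 = 0.01429. The true SE is 1.050 times the reported one. Coverage of the 90% interval is 2Φ(1.645/1.050) − 1 = 88.3%, and one-sided Type I error is 5.9%.
- 10% missing: 1/63 + (7/4900)(1 − 1/63) = 0.01728. The ratio is 1.100, coverage 86.5% and Type I error 6.7%.

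Simulation with age-by-sex donor cells agrees: coverage 88.0% and 86.5%, Type I error 5.8% and 7.0%. With donors by randomised arm and ten draws combined, coverage is 89.7% and 89.8%, and Type I error 5.1% and 5.7%.

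**3. Donor cells.** If age is taken in whole years, 4 × 2 × 2 = 16 cells, and 132/16 is about 8 completers in each.

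**The case against.** Six points can be made for the plan.

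- **A reader might infer that the analysis is no longer as randomised.** The text does not support that. No imputed child changes arm; only the source of the borrowed value depends on treatment received. What remains is that the borrowed value can come from the other randomised arm.
- **The 25% rule is written for the As-Treated set only.** Sections 6.3 and 6.6.1.3 do not cite it. The exchange of donors is therefore conditional on that rule, but the SAP offers no other way to establish what a child received.
- **Choosing donors by actual exposure can be defended**, since a non-user may well resemble a control. That is a different assumption about the missing values. If it is wanted, it should be stated as such, and it remains unsafe for a noninferiority test.
- **A reader might infer that the fallback is single imputation.** The documents do not say so. It stands in a section on multiple imputation with ten data sets, and a random draw can be repeated. The coverage loss in step 2 of the working applies only to the one-draw reading. The wording leaves the matter open because the ten data sets are tied to the imputation models and the fallback replaces the model.
- **The fallback may never run.** Clinical significance alone is enough to keep a covariate, so the trigger is narrow. This also means that there is no established case for removing the trigger.
- **The analysis is supportive.** Success rests on tests without imputation, and at the planned 5% loss the effects are small. Both statements are correct and limit the weight of the point.

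**Conclusion.** The point holds as a conflict between the donor rule in 6.3 and 6.6.1.3 and the ITT definition in 6.2, together with an unclear statement on repetition.

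Its main consequence is for the fellow-eye noninferiority check. With half of the missing device children drawing from controls and a true difference at the margin, one-sided Type I error is about 7% to 8% at 5% missing and 8% to 9% at 10%. This depends on the As-Treated rule defining treatment received, on the assumed half, and on outcomes within an arm not depending on use. For efficacy the same mechanism costs about 0.002 to 0.004 logMAR and is cautious. If, and only if, a single draw is meant, the 90% interval also falls short by about 2 points of coverage at 5% missing and 3.5 at 10%.

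It is a minor correction, worth making because this analysis is the plan's named check on missing data for both co-primary endpoints.

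**What to change.** In SAP 6.3 and 6.6.1.3, form the donor groups by randomised arm, age and sex in place of treatment received. State that the draw is repeated in each of the ten data sets and that the results are combined by the multiple-imputation rules already named there. Section 6.6.2 inherits the change. Drawing from a bootstrap sample of the donors, and a line on what is done when a cell has few or no donors, would be useful refinements but are not essential.

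The cost is one or two sentences and little programming. If a single draw had been intended, the supportive interval becomes slightly wider: at 5% missing the mean half-width for efficacy is 0.0400 logMAR with ten draws against 0.0391 with one. The primary analysis, the sample size of 132/140 and the success rule stay as they are.
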